6.1.1.2. Sensitivity/Supplementary Analyses

6.1.1.2.1. Supplementary Analysis 1

- Estimand strategy: Estimand 3, treatment policy + composite estimand ([Section 2.1.3](#)).
- This supplementary analysis will use the same analysis set, analysis methodology and summary as the main analysis.
- Intercurrent events and missing data: The intercurrent event is captured through the variable definition; for participants who drop out for any reason, the response will be defined as “non-responsive” after that point.

6.1.1.2.2. Supplementary Analysis 2

- Estimand strategy: Estimand 4, treatment policy estimand (Section 2.1.4).
- Analysis set: FAS (Section 4). Participants must have baseline PP-NRS ≥ 4 to be included.
- Analysis methodology: multiple imputations (Section 5.3.1) including data from Weeks 2, 4, 8, 12, 16, 20 and 26; CMH method will be used for analyzing the imputed datasets; Rubin's rule will be used to combine the multiple estimates and standard errors across the imputed datasets and provide p-values.
- Intercurrent events and missing data: all data will be used regardless of rescue therapy; missing values will be handled through multiple imputations (Section 5.3.1).
- The number of participants, the number and percent of participants with missing response imputed, and the estimate of response percentage at Week 2 along with the corresponding 95% confidence interval will be presented for each treatment arm.
- The estimate of the difference in proportions of response at Week 2 along with the corresponding p-value and 95% confidence interval will be presented for abrocitinib versus dupilumab.

6.1.1.2.3. Supplementary Analysis 3

- The analysis will assess the endpoint on the analyses set FAS with baseline PP-NRS ≥ 4 and baseline EASI ≥ 16 . It will use the same methodology, intercurrent events, missing data handling method and summary as the main analysis.

6.1.2. Week 4 EASI-90 Response

6.1.2.1. Main Analysis

- Estimand strategy: Estimand 1, composite estimand (Section 2.1.1).
- Analysis set: FAS (Section 4).
- Analysis methodology: CMH and normal approximation in Section 5.2.1.
- Intercurrent events and missing data: The intercurrent event is captured through the variable definition; for participants who drop out for any reason or use rescue therapy, the response will be defined as "non-responsive" after that point.
- The number of participants, number and percent of response at Week 4 along with the 95% confidence interval by normal approximation will be presented for each treatment arm.

- The CMH test p-value, the estimate of the difference in proportions of response at Week 4 along with the 95% confidence interval by CMH normal approximation will be presented for abrocitinib versus dupilumab.

6.1.2.2. Sensitivity/Supplementary Analyses

6.1.2.2.1. Supplementary Analysis 1

- Estimand strategy: Estimand 3, treatment policy + composite estimand (Section 2.1.3).
- This supplementary analysis will use the same analysis set, analysis methodology and summary as the main analysis.
- Intercurrent events and missing data: The intercurrent event is captured through the variable definition; for participants who drop out for any reason, the response will be defined as “non-responsive” after that point.

6.1.2.2.2. Supplementary Analysis 2

- Estimand strategy: Estimand 4, treatment policy estimand (Section 2.1.4).
- Analysis set: FAS (Section 4).
- Analysis methodology: multiple imputations (Section 5.3.1) including data from Weeks 2, 4, 8, 12, 16, 20 and 26; CMH method will be used for analyzing the imputed datasets; Rubin’s rule will be used to combine the multiple estimates and standard errors across the imputed datasets and provide p-values.
- Intercurrent events and missing data: all data will be used regardless of rescue therapy; missing values will be handled through multiple imputations (Section 5.3.1).
- The number of participants, the number and percent of participants with missing response imputed, and the estimate of response percentage at Week 4 along with the corresponding 95% confidence interval will be presented for each treatment arm.
- The estimate of the difference in proportions of response at Week 4 along with the corresponding p-value and 95% confidence interval will be presented for abrocitinib versus dupilumab.

6.1.2.2.3. Supplementary Analysis 3

- The analysis will assess the endpoint on the analyses set FAS with baseline EASI \geq 16. It will use the same methodology, intercurrent events, missing data handling method and summary as the main analysis.

6.2. Secondary Endpoint(s)

6.2.1. Key Secondary Endpoint - Week 16 EASI-90 Response

6.2.1.1. Main Analysis

- Estimand strategy: Estimand 1, composite estimand ([Section 2.1.1](#)).
- Analysis set: FAS ([Section 4](#)).
- Analysis methodology: CMH and normal approximation in [Section 5.2.1](#).
- Intercurrent events and missing data: The intercurrent event is captured through the variable definition; for participants who drop out for any reason or use rescue therapy, the response will be defined as “non-responsive” after that point.
- The number of participants, number and percent of response at Week 16 along with the 95% confidence interval by normal approximation will be presented for each treatment arm.
- The CMH test p-value, the estimate of the difference in proportions of response at Week 16 along with the 95% confidence interval by CMH normal approximation will be presented for abrocitinib versus dupilumab.

6.2.1.2. Sensitivity/Supplementary Analysis

6.2.1.2.1. Supplementary Analysis 1

- The analysis will assess the endpoint on the analysis set PPAS ([Section 4](#)). It will use the same methodology, intercurrent events, missing data handling method and summary as the main analysis.

6.2.1.2.2. Supplementary Analysis 2

- Estimand strategy: Estimand 3, treatment policy + composite estimand ([Section 2.1.3](#)).
- This supplementary analysis will use the same analysis set, analysis methodology and summary as the main analysis.
- Intercurrent events and missing data: The intercurrent event is captured through the variable definition; for participants who drop out for any reason, the response will be defined as “non-responsive” after that point.

6.2.1.2.3. Supplementary Analysis 3

- Estimand strategy: Estimand 4, treatment policy estimand ([Section 2.1.4](#)).
- Analysis set: FAS ([Section 4](#)).

- Analysis methodology: multiple imputations ([Section 5.3.1](#)) including data from Weeks 2, 4, 8, 12, 16, 20 and 26; CMH method will be used for analyzing the imputed datasets; Rubin's rule will be used to combine the multiple estimates and standard errors across the imputed datasets and provide p-values.
- Intercurrent events and missing data: all data will be used regardless of rescue therapy; missing values will be handled through multiple imputations ([Section 5.3.1](#)).
- The number of participants, the number and percent of participants with missing response imputed, and the estimate of response percentage at Week 16 along with the corresponding 95% confidence interval will be presented for each treatment arm.
- The estimate of the difference in proportions of response at Week 16 along with the corresponding p-value and 95% confidence interval will be presented for abrocitinib versus dupilumab.

6.2.2. Secondary Endpoints

6.2.2.1. Binary Endpoints

- Endpoints:
 - Weeks 2, 8, 12, 20 and 26 EASI-90 Response;
 - Weeks 2, 4, 8, 12, 16, 20 and 26 EASI-75, IGA Response based on score of clear (0) or almost clear (1) (on a 5-point scale) and a reduction from baseline of ≥ 2 points;
 - PP-NRS4 Response each day from Days 2-15, Weeks 4, 8, 12, 16, 20 and 26.
 - Weeks 2, 12, 16, 20 and 26 DLQI ≥ 4 Points Improvement from Baseline Response
- Estimand strategy: Estimand 1, composite estimand.
- Analysis set: FAS ([Section 4](#)). Participants must have baseline PP-NRS ≥ 4 to be included in the analysis for PP-NRS4. Participants must have baseline DLQI ≥ 4 to be included in the analysis for DLQI response.
- Analysis methodology: CMH and normal approximation in [Section 5.2.1](#).
- Intercurrent events and missing data: The intercurrent event is captured through the variable definition; for participants who drop out for any reason or use rescue therapy, the response will be defined as "non-responsive" after that point.
- The number of participants, number and percent of response at each specified Weeks along with the 95% confidence interval by normal approximation will be presented for each treatment arm.

- The CMH test p-value, the estimate of the difference in proportions of response at each specified Weeks along with the 95% confidence interval by CMH normal approximation will be presented for abrocitinib versus dupilumab.

6.2.2.2. Continuous Endpoints

- Endpoints:
 - Weeks 2, 4, 8, 12, 16, 20 and 26 Percent Change from Baseline in %BSA, SCORAD;
 - Weeks 12, 16 and 26 Change from Baseline in HADS;
 - Weeks 2, 12, 16, 20 and 26 Change from Baseline in DLQI;
 - Weeks 12, 16 and 26 Change from Baseline in EQ-5D-5L, POEM, MOS-Sleep Scale;
 - Weeks 2, 12, 16, 20 and 26 Change from Baseline in Skin Pain NRS.
- Estimand strategy: Estimand 2, hypothetical estimand ([Section 2.1.2](#)).
- Analysis set: FAS ([Section 4](#)). Participants must have observed baseline measure to be included in the corresponding analysis.
- Analysis methodology: MMRM ([Section 5.2.3](#)) including change from baseline or percent change from baseline data from the corresponding weeks.
- Intercurrent events and missing data: drop-out for any reason and use of rescue therapy are the intercurrent events; data after dropout or use of rescue therapy at any time during the treatment period will be set as missing; only observed data will be used.
- Number of participants included in the analysis will be presented for each treatment arm.
- The least square mean (LSM) of change from baseline or percentage change from baseline along with the corresponding 95% confidence interval will be presented for each treatment arm at each specified time points.
- The LSM difference along with the corresponding p-value and 95% confidence interval will be presented for abrocitinib versus dupilumab at each specified time points.

6.2.2.3. Time from baseline to achieve at least a 4-point improvement in the severity of PP-NRS scale

- Analysis set: FAS (Section 4). Participants must have baseline PP-NRS ≥ 4 to be included.
- Analysis methodology: analysis of time to event endpoint (Section 5.2.5).
- Intercurrent events and missing data: PP-NRS observations will first be censored by use of rescue therapy; for all participants who have not experienced the event, their time to event will be right censored at the last available measurement time.
- The number of participants, number and percent of participants censored and participants with PP-NRS4 Response will be provided for each treatment arm.
- Estimated survival curves using the Kaplan-Meier method and number of patients at risk will be displayed graphically for each treatment arm. The 25%, 50% and 75% quartiles with their 95% confidence intervals will also be presented for each treatment arm.
- The log-rank test (stratified using baseline disease severity) p-value will be presented for abrocitinib versus dupilumab.

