1.2. Schema

1.3. Schedule of Activities (SoA)

The SoA table provides an overview of the protocol visits and procedures. Refer to the relevant noted sections of the protocol for detailed information on each procedure and assessment required for compliance with the protocol.

The investigator may schedule visits (unplanned visits) in addition to those listed in the SoA table, in order to conduct evaluations or assessments required to protect the well-being of the participant.

Procedure	Screening	Study Intervention Period									EOT / ED Visit	EOS Follow-up Visit (4 weeks after ED/EOT)	Notes
		1	2	3	4	5	6	7	8	9			
Visit		D1	D8	D15	D29	D57	D85	D113	D141	D169	D183	D211	
Study Day		WK0	WK1 Call	WK2	WK4	WK8	WK12	WK16	WK20	WK24 Call	WK26	WK30	
Study Week													
Visit Window (Days)	-28	0	±1	±1	±2	±3	±3	±3	±3	±3	±3	±3	
Enrollment													
Informed consent	X												Refer to Section 10.1.3 in Appendix 1 .
Register participant in IRT system	X												
Inclusion/Exclusion Criteria	X	X											Refer to Section 5.1 and Section 5.2 for Inclusion and Exclusion Criteria, respectively.
Demographics: Medical, Tobacco, Alcohol, and Atopic Dermatitis (AD) Disease Histories	X												Any previous history of intolerance/allergy to any drug, regardless of indication. AD disease history includes collection of AD diagnosis and duration
Review Prior/Concomitant Medications & Treatments	X	X	X	X	X	X	X	X	X	X	X	X	

Procedure	Screening	Study Intervention Period									EOT / ED Visit	EOS Follow-up Visit (4 weeks after ED/EOT)	Notes
		1	2	3	4	5	6	7	8	9			
Visit		D1	D8	D15	D29	D57	D85	D113	D141	D169	D183	D211	
Study Day		WK0	WK1 Call	WK2	WK4	WK8	WK12	WK16	WK20	WK24 Call	WK26	WK30	
Study Week													
Visit Window (Days)	-28	0	±1	±1	±2	±3	±3	±3	±3	±3	±3	±3	
Dispense eDiary and instruct participants on use	X												
Train/check understanding of participants on protocol guidance for background medicated and non-medicated topical therapy and daily recording in eDiary		X	X	X	X	X	X	X	X	X	X		Refer to Section 6.5.1 .
Collect eDiary											X	X	Collect the eDiary at Week 26/EOT for participants who rollover into the B7451015 long-term extension study. Collect the eDiary from all other participants at Week 30/EOS (or at the last visit a participant will have if ED).
Provide Participant Emergency Contact Card	X												
Medical Procedures													
Complete Physical Exam	X	X										X	Refer to Section 8.2.1

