8.1.6.1. Peak Pruritus Numerical Rating Scale (PP-NRS)

The severity of itch (pruritus) due to AD will be assessed using the PP-NRS, a validated horizontal NRS.^{22,23} Participants will be asked to assess their worst itching due to AD over the past 24 hours on an NRS anchored by the terms “no itch” (0) and “worst itch imaginable” (10). This item will be administered to all participants. Participants will enter the PP-NRS assessment into an eDiary on a daily basis from the Screening visit through the Week 30 visit.

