5.2.5. Analyses for Time-to-Event Endpoints

For a participant who experiences the event, the time to event will be the study day corresponding to the actual date of the event or the earliest visit date at which the participant has already experienced the event. For all participants who have not experienced the event, their time to event will be right censored at the last available measurement time (or visit) used to define whether the participant experienced the associated event.

Time-to-event endpoints will be summarized using the Kaplan-Meier method and estimated survival curves will be displayed graphically. Graphs will describe the number of patients at risk over time. The median and quartiles will be estimated by the Kaplan-Meier method. 95% CIs for the median and quartiles will also be provided.

The log-rank test (stratified using baseline disease severity) p-value will be used for comparing time to event data between treatment groups.

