Appendix 2. Definition and Use of Visit Windows in Reporting

Unless otherwise specified, visit windows will be used for efficacy variables, and for any safety data that display or summarize by study visit. For other endpoints (eg, ECG, vital signs), visit windows will be applied for summary statistics by study visits if required.

Visit Label	Target Day	Definition [Day window]
Screening		Days -28 to Day -1
Baseline	Day 1 (Day of first dose), Baseline	Day 1
Week 2	15	Days 2 to 22
Week 4	29	Days 23 to 43
Week 8	57	Days 44 to 71
Week 12	85	Days 72 to 99
Week 16	113	Days 100 to 127
Week 20	141	Days 128 to 155
Week 24	169	Days 156 to 176
Week 26	183	Days 177 to 197
Follow Up/End of Study		
Week 30	-	Days 198 to -

If there are both observed records and missing records within the same visits window, the observed record will be used.

For the lab values, if the calculated study day for the labelled baseline visit is not study Day 1 but falls within 28 days before the start of the study dosing, then that data should be used for the baseline instead of leaving baseline missing.

For the other values, if the calculated study day for the labelled baseline visit is not study Day 1, but falls before the start of the study dosing, then that data should be used for the baseline instead of leaving baseline missing.

If two or more visits fall into the same window, keep the one closest to the Target Day. If two visits are equaled distant from the Target Day in absolute value, the later visit should be used.

If two or more values are collected on the same day: for measurements with labeled visits, the value where collect visit = analysis visit will be used; for measurements without labeled

visits but with time of collection, the last measurement of the day will be used for the analysis.

PP-NRS is recorded every day throughout the study. Observations on the actual day will be used to analyze Days 2-15 PP-NRS, and to derive the time to achieve PP-NRS4 response. Weeks 2, 4, 8, 12, 16, 20 and 26 PP-NRS response will be based on the windowing method.

Safety analysis may follow Pfizer standards.

For Estimand 1 and 2, data after rescue therapy will be censored first. The remaining observation will be mapped to the analysis visits.

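### Time to PP-NRS4 response has no end-of-treatment cut, so a first response after Week 26 in completers who do not enter the extension can count as an event

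*SAP*

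**What the plan says.** SAP 6.2.2.3 gives two data rules for this endpoint. The first is that "PP-NRS observations will first be censored by use of rescue therapy". The second is that, for participants without an event, "their time to event will be right censored at the last available measurement time". The general time-to-event method in SAP 5.2.5 has the same end point for censoring. SAP Appendix 2 takes the data from the daily diary: "Observations on the actual day will be used to analyze Days 2-15 PP-NRS, and to derive the time to achieve PP-NRS4 response". It gives no last day for the time-to-event use.

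Protocol 8.1.6.1 sets the diary period: "Participants will enter the PP-NRS assessment into an eDiary on a daily basis from the Screening visit through the Week 30 visit". The Schedule of Activities (Protocol 1.3) splits it: "Collect the eDiary at Week 26/EOT for participants who rollover into the B7451015 long-term extension study". Other participants hand the diary back at Week 30, or at their last visit if they leave early.

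Treatment ends at Week 26, with the last injection at Week 24 (Protocol 4.1). The four-week post-treatment period is for participants who do not enter the extension (Protocol 6.1.1).

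SAP Section 4 has a default rule that censors observations after dropout or rescue, unless a section specifies otherwise.

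**The concern.** A participant who completes Week 26, was never rescued and does not enter the extension is neither a dropout nor a rescue case. No rule in the SAP removes that person's ratings between the Week 26 and Week 30 visits. If the first 4-point improvement falls there, it is an event for a treatment-response endpoint although study drug has ended.

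Who is still observed in that period depends on extension eligibility and choice. The Kaplan-Meier method applies the event fraction seen in this subset to everyone in the arm who has not yet responded, including those censored at rollover. A few events can therefore move the tail. The responder count and the log-rank p-value take in the same events.

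The cut looks omitted rather than chosen. The next endpoint, topical-therapy-free days (SAP 6.2.2.4), stops at the last day of exposure. The by-visit binary and continuous endpoints end with Week 26 (SAP 6.2.2.1 and 6.2.2.2), and the weekly average of this same diary item ends on Day 183 (SAP Appendix 8.1.1). SAP 6.2.2.3 names no estimand that would call for off-drug data.

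**Working it through.** **The plan's own figure.** The documents give no power, event count or hazard ratio for this endpoint. The nearest figure is Week 2 PP-NRS4 power: 11% against 36% (11% plus 25 points), 300 per arm, two-sided 5%. A two-proportion calculation gives more than 99.99%, consistent with the stated 99% or more. It says nothing about the tail of the curve.

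**Calendar.** Week 26 is Day 183 and Week 30 is Day 211, so 211 − 183 = 28 off-drug diary days for completers who do not roll over. Early stoppers have an end-of-treatment visit within 7 days of the last dose and then 28 days of follow-up (Protocol 7.3), so up to about 7 + 28 = 35 days.

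**Events and curve.** The documents give none of the next three inputs, so all are assumptions shown over a range:
- R: share with a response by Day 183 (70% to 95%)
- s: share of never-responders who do not roll over (10% to 50%)
- q: chance that such a person has a first response off drug (5% to 40%)

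Extra events per arm = 300 × (1 − R) × s × q. Kaplan-Meier response at Day 211 = R + (1 − R) × q, which does not depend on s.

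| R | s | q | Extra events per arm | Curve, Day 183 to Day 211 |
|---|---|---|---|---|
| 95% | 10% | 5% | 0.1 | 95% to 95.25% |
| 90% | 30% | 20% | 1.8 | 90% to 92% |
| 80% | 30% | 20% | 3.6 | 80% to 84% |
| 70% | 30% | 20% | 5.4 | 70% to 76% |
| 70% | 50% | 40% | 18 | 70% to 82% |

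With R above 75% all three quartile estimates fall on treatment and stay as they are. In the fourth row the 75% quartile would be reported only because of off-drug days. The median is touched only if R is below 50%.

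**Log-rank.** Simulation with 300 per arm, 100 runs per scenario, Week 2 response 11% and 36%, unstratified (the plan stratifies), and no dropout or rescue before Day 183. Pairs are dupilumab/abrocitinib.

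| R | s | q | Mean Z with Day 183 cut | Mean Z without |
|---|---|---|---|---|
| 90/92% | 30% | 10/10% | 3.24 | 3.25 |
| 80/85% | 30% | 20/5% | 3.66 | 3.54 |
| 70/75% | 30% | 20/5% | 3.06 | 2.86 |
| 70/75% | 50% | 40/40% | 3.18 | 3.08 |
| 70/75% | 50% | 40/10% | 3.22 | 2.46 |

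The mean shift is about 0.2 or less when s is 30%, and 3.22 − 2.46 = 0.76 in the most extreme unequal case. Early stoppers were not modelled.

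**The case against.** The strongest reply is that the affected group is very narrow. A person must complete Week 26, never be rescued, not enter the extension, and have had no qualifying day in six months of daily ratings. Persistent itch non-responders are plausibly the likeliest to have been rescued or to have left, so the counts above, which start from the full 300 per arm, lean high. SAP 6.2.2.3 reports counts, curves and quartiles, not a terminal response rate, and numbers at risk are shown, so a thinning tail is visible. The endpoint is outside the testing sequence in SAP 5.1, and SAP 5.2 bars significance claims for it. All of this stands and limits the size of the problem. None of it supplies the missing cut.

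Four stronger readings are tempting, but the documents do not support them.

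- A reader might infer that off-drug days in general are counted as treatment response. They are not: on-treatment responders already have their event, and only a first-ever response after treatment adds one. The 28 of 211 days (13%) is therefore not a measure of bias.
- A reader might infer that everyone outside the extension rates until Day 211. Early leavers return the diary at their last visit, which for most is well before then, and the default rule in SAP Section 4 may remove their later ratings. Whether it does is unclear: SAP 6.2.2.3 mentions only rescue, and dropout is not defined for someone who stops treatment but stays in follow-up.
- A reader might infer a larger shift in one arm. That needs unequal off-drug response rates, and the documents give no reason to assume them.
- A reader might infer that different residual drug cover biases the comparison. A Week 24 injection on a two-week interval and tablets to Week 26 finish together on schedule. Anything beyond that needs pharmacokinetic facts that the documents do not give.

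**Conclusion.** The gap is real and minor. As written, the rule lets a first-ever off-drug improvement in Week 26 completers who do not roll over enter the responder count, the tail of the curve and the log-rank test. The default dropout rule does not reach these participants.

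Under the assumed ranges this is about 0.1 to 18 extra events per arm, with about 2 in the 90%/30%/20% case, and a mean log-rank shift of about 0.2 in Z or less in the moderate scenarios. Medians are unlikely to move, and quartile estimates do not move if on-treatment response exceeds 75%. The direction of any shift cannot be told from the documents. Neither the primary nor the key secondary conclusions are affected.

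**What to change.** Add to SAP 6.2.2.3 that, besides the rescue rule, PP-NRS observations after the Week 26/EOT visit are not used, and that participants without an event are censored at their last rating on or before that visit. State that the dropout rule in SAP Section 4 applies to this endpoint, and say whether dropout includes stopping treatment while remaining in follow-up. Display the curve to Week 26 only.

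Tying the cut to the visit is safer than a fixed Day 183 or the last dose. The visit may fall as late as Day 186 (183 + 3), so a Day 183 cut could drop on-treatment ratings. Last dose is ambiguous between the final injection (Week 24, Day 169) and the tablets (Week 26).

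The cost is a few sentences in the SAP, a line of code, and the loss of a few late off-drug events. Making the change before unblinding also avoids choosing a cut-off after the data are seen.
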